- a Patients who do not meet the criteria for participation in this trial (screen failure) may be rescreened once. Patients must re-sign the ICF prior to re-screening, if the screening period exceeds 21 d. For both screening and re-screening, results of radiology scans performed prior to obtaining informed consent and within 28 d prior to randomization may be used. However, in case of signs of rapid progression, a new tumor evaluation may be necessary to obtain a reliable baseline assessment.
- b Patients who discontinue trial treatment for whatever reason, will return to the clinic for EoT visit within 21 d after last dose. The visit at which response assessment shows (confirmed) progressive disease may be used as the EoT visit. The EoT visit and post-treatment follow-up period will only be performed after discontinuation of both trial drugs. The EoT visit and post-treatment follow-up period for patients in Arms 2 and 3 who will continue to receive add-on therapy will be performed as outlined in SOA2 (Section 1.3.2).
- c All AEs will be reported until 90 d after the last dose of trial treatment or until a new anti-cancer therapy is started. Additionally, in case a new anti-cancer therapy is started within 90 d after last treatment, the safety follow-up visit should be performed just prior to starting the new anti-cancer therapy. Adverse events after start of new anti-cancer therapy do not need to be reported unless a causal relationship to BNT111-01 or cemiplimab is suspected.
- d Patients who discontinue trial therapy prior to disease progression should continue to have regular efficacy assessments as scheduled per protocol, until disease progression, the start of next-line anti-cancer therapy, withdrawal of consent, or death, whichever occur first.

^{*} Visits C1D8, C1D15, C2D8, and C2D15 are not to be conducted in patients in Arm 3 (cemiplimab only).

Clinical Trial Protocol BNT111-01

Page 18 of 133 Version: 7.0 Date: 09 FEB 2023

- After the last trial visit, information on survival status and new anti-cancer therapy will be collected via phone calls, patient medical records, and/or clinic visits approximately every 3 mon until death (unless the patient withdraws consent for survival follow-up or the sponsor terminates the trial). If a patient asks to be withdrawn from survival follow-up, this request must be documented in the source documents and signed by the investigator.

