- f "n" represents the number of the respective cycle (e.g., C4 means fourth cycle of treatment).
- g Visit CnD1 should occur 21 (± 3) d after the first day (i.e., treatment visit) of the previous cycle.
- h Informed consent must be documented before any trial-specific screening procedure is performed.
- i Eligibility should be confirmed and documented in the eCRF. This should be performed when all screening results are available and within 21 d after initiation of screening.
- j Underlying disease history should include histology, TNM stage at diagnosis (including which AJCC edition), prior anti-cancer therapies/procedures, date of last progression.
- k BRAF V600 mutation status may be obtained from medical history data.
- TNM staging at the time of trial entry to be performed according to AJCC 8th edition.
- m Concomitant medication and therapy includes any therapies (e.g., prescription drugs, over-the-counter drugs, vaccines, herbal or homeopathic remedies, nutritional supplements) used by a patient in addition to protocol-mandated trial treatment from 28 d prior to initiation of trial treatment until the SFU2 visit.
- n Vital signs (body temperature, pulse rate, respiratory rate, and blood pressure) should be measured within 60 min prior to the administration of the trial treatment(s) and at 30 (±10) min, 60 (±10) min, 4 h (±10 min), and 6 h (±10 min) after administration, or if clinically indicated (see Section 8.2.3 for guidelines on reduction or expansion of these time points).
- o At screening and at EoT assessments must include a full physical examination. Record abnormalities observed on the respective eCRF pages as appropriate. For all subsequent physical examinations perform a limited, symptom-directed examination at specified time points and as clinically indicated at other time points. Record new or worsened clinically significant abnormalities on the AE eCRF.
- p Single 12-lead ECG recordings will be obtained during screening, at EoT, and as clinically indicated at other time points. Patients should be resting in a supine position for ≥ 10 min prior to ECG recording. The interpretation of the ECG recording will be done locally by the investigator.

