- y Hematology assessment should be performed at screening, ≤ 24 h prior to each drug administration, on treatment discontinuation, and at 30 d SFU1 or if clinically indicated (see Section 10.2 for assessments to be done). Samples should be assessed by both the central and local laboratory. Results of local laboratory assessments need to be reviewed prior to drug administration. Unscheduled assessments can be performed locally, or sent to the central laboratory.
- z Serology assessments for patients will include HBsAG, anti-HBc, anti-HBs and anti-HCV. HIV (1/2) testing required if the patient has never been tested for HIV or if testing was prior to primary cancer diagnosis or performed ≥ 12 mon prior to trial start. Samples should be shipped to a central laboratory.
- aa Chemistry panel should be performed at screening, ≤ 24 h prior to each drug administration, on treatment discontinuation, and at 30 d SFU1 or if clinically indicated (see Section 10.2 for assessments to be done). Samples should be assessed by both the central and local laboratory. Results of local laboratory assessments need to be reviewed prior to drug administration. Unscheduled assessments can be performed locally, or sent to the central laboratory.
- bb Coagulation assessments to be performed at screening, at EoT and if clinically indicated (see Section 10.2 for assessments to be done). Samples should be shipped to a central laboratory; unscheduled assessments can be performed locally.
- cc TSH and free T4 will be assessed at screening, once every two cycles, on treatment discontinuation, at SFU1, and as clinically indicated. Samples should be shipped to a central laboratory and, if required, to the local laboratory. Unscheduled assessments can be performed locally, or sent to the central laboratory.
- dd All WOCBP will have a serum pregnancy test at screening, within 10 d prior to initiation of trial treatment. Urine or serum pregnancy test will be performed at the start of every cycle (starting from Cycle 2) or according to local requirements (in cases where more frequent testing is required) and at EoT and SFU1. If a urine pregnancy test is positive, hold dosing and confirm the result with a serum pregnancy test.
- ee For urinalysis assessments dipsticks are to be used, microscopic evaluation should be performed per investigator's discretion. Tests will be done locally with material provided by the central laboratory.

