3.2 Trial design

This is an open-label, randomized, multi-site, Phase II, interventional trial designed to evaluate the efficacy, tolerability, and safety of BNT111 + cemiplimab in anti-PD1/PD-L1 refractory/relapsed patients with unresectable Stage III or IV melanoma. The contributions of BNT111 and cemiplimab will be delineated in single agent calibrator arms (Arms 2 and 3). Patients in Arms 2 and 3, who experience centrally verified (BICR) disease progression under single agent treatment, may be offered addition of the respective other compound to the ongoing treatment after re-consent.

Randomization will be stratified by metastatic status (M0, M1a, M1b vs. M1c, M1d) and number of prior lines of systemic treatment (1 vs 2 to 5).

Screening period:

Screening procedures will be performed within 21 days before the start of treatment on Day 1 of Cycle 1.

Treatment period:

Patients will be randomized in a 2:1:1 ratio to Arm 1 (BNT111 + cemiplimab) and calibrator Arm 2 (BNT111 monotherapy) and Arm 3 (cemiplimab monotherapy).

Treatments with BNT111 will be given once weekly for the first 6 weeks, followed by treatments once every 3 weeks (±3 d). Cemiplimab will be given once every 3 weeks (±3 d) throughout the trial.

The treatment period starts on Day 1 of Cycle 1 and continues for up to 24 months or until confirmed progression of disease, withdrawal of consent or unacceptable toxicity. Treatment with cemiplimab and/or BNT111 may be continued through initial radiological disease progression until symptomatic disease progression or unacceptable toxicity.

If one of the compounds needs to be discontinued, single agent treatment with the other can continue upon investigator's and sponsor's agreement.

Efficacy is assessed with regular efficacy assessments every 6 weeks for the first 3 months after treatment start, then every 9 weeks for the next 9 months and every 12 weeks thereafter until progressive disease, start of new anti-cancer therapy, withdrawal of consent, death or lost to follow-up.

Add-on therapy for patients in Arm 2 or 3

Patients who experience centrally verified (BICR) disease progression under monotherapy may continue with add-on therapy after re-consent.

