An analysis update will be performed when the last patient discontinued from the trial and once all patients have been randomized and have been followed-up for at least 24 months. An analysis update may be subsequently performed.

Statistical Analysis Plan (SAP) BNT111-01

Page 30 of 78 Version: Final v7.0 Date: 05Mar2024

Data up to and including the clinical cut-off date will be taken into account for the statistical analysis.

All analyses will be conducted using SAS® version 9.4 or higher.

Baseline is defined as last non-missing value prior to the first dose of trial treatment at C1D1. Assessments performed at C1D1 will be considered for baseline value, unless there is evidence the assessment was performed after trial treatment had been administered. For the add-on treatment if the baseline visit and AOC1D1 are on the same day, the assessment only needs to be taken once. In this case the AOC1D1 would be considered as the baseline value, unless there was evidence that the assessment was done after treatment had been administered.

To identify the baseline value, generally, if there are multiple assessments available for a particular day, the assessment that is closest to the day (and time if collected) of the first dose of the trial treatment (i.e., BNT111 or cemiplimab) will be used as the baseline value in the summary/analyses.

Multiple values at post-baseline visits: if there are multiple post-baseline assessments available within a visit/day, the first value and corresponding date/time will be considered.

Change from baseline will be calculated as follows:

Change from baseline = post-baseline assessment value – baseline assessment value.

If either the baseline or post-baseline assessment value is missing, the change from baseline is set to missing as well.

Duration (Other than "trial treatment duration" defined in Section 8.5.1) will be calculated as follows:

Duration = last observation date - first observation date + 1

For conversion of days to months or years the following rules will be applied:

- 1 month = 30.4375 days
- 1 year = 365.25 days

Trial Day and Treatment Day are defined as follows:

- Trial day:
 - If assessment date < randomization date then trial day = assessment date randomization date
 - If assessment date >= randomization date then trial day = assessment date randomization date + 1
- Treatment Day = treatment date date of first dose +1

That is, trial day 1 indicates the date of treatment initiation.

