8.5.3 Laboratory assessments

Clinical laboratory data will be summarized for Safety analysis set and the Add-on Treatment set (as applicable).

Clinical laboratory data to be summarized includes hematology (for IAs, only Hemoglobin, White Blood Cells (WBC), Absolute Lymphocytes Count, Absolute Neutrophils Count, and Platelets will only be presented). For CSR, all parameters planned as per protocol will be presented), clinical chemistry (for IAs, only Total Bilirubin, Aspartate aminotransferase (AST), Alanine aminotransferase (ALT), Lipase, Lipase pancreatic, Amylase, Creatine kinase and Creatinine will be presented. For CSR, all parameters planned as per protocol will be presented), and urinalysis. The safety laboratory parameters to be assessed are listed in Section 10.2 of the protocol amendment. The scheduled time points for assessment are outlined in the SoAs (Section 10.4).

Safety laboratory parameters at each visit and change from baseline to each post-baseline visit will be summarized using descriptive summary statistics for each parameter by treatment group.

If a laboratory value is reported using a nonnumeric qualifier e.g., less than (<) a certain value, or greater than (>) a certain value, the given numeric value will be used in the summary statistics, ignoring the nonnumeric qualifier.

In case there are several results for the same parameter at the same visit, the record from the central lab will be used for the analyses. The local lab results will be only listed.

Safety laboratory results will be classified according to the most recent version of NCI-CTCAE. Shift tables from baseline to worst grade on treatment will be provided for each laboratory parameter by randomized treatment group.

Laboratory values that are below or above the reference ranges will be flagged.

Abnormal and clinically significant, abnormal and not clinically significant and normal laboratory values will be summarized for each urinalysis parameter by visit and randomized treatment group.

In addition, clinically laboratory values for each parameter will be plotted using trellis plots. Maximum post baseline values will be displayed vs baseline value by treatment group. The

Statistical Analysis Plan (SAP) BNT111-01

Page 50 of 78 Version: Final v7.0 Date: 05Mar2024

plots will be repeated for minimum post baseline values vs baseline value by treatment group.

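### The worst-grade laboratory shift table compares six early scheduled draws in Arms 1 and 2 with two in Arm 3, which tilts short-lived hematology and chemistry findings toward a milder grade in Arm 3

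*Protocol*

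**What the plan says.** In the protocol's schedule of activities (section 1.3.1, SOA1), hematology and blood chemistry are marked at C1D1, C1D8, C1D15, C2D1, C2D8, C2D15 and at Day 1 of each cycle from Cycle 3. The notes tie both panels to dosing: "Hematology assessment should be performed at screening, ≤ 24 h prior to each drug administration" and "Chemistry panel should be performed at screening, ≤ 24 h prior to each drug administration". The asterisked note then removes four of these visits in one arm: "Visits C1D8, C1D15, C2D8, and C2D15 are not to be conducted in patients in Arm 3". SAP Appendix 4 repeats it. From Cycle 3 on the arms share a schedule, since "Visit CnD1 should occur 21 (± 3) d after the first day" of the previous cycle.

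SAP 8.1 sets the reference value: "Baseline is defined as last non-missing value prior to the first dose of trial treatment at C1D1". The C1D1 draw is therefore not a post-baseline value.

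SAP 8.5.3 states: "Shift tables from baseline to worst grade on treatment will be provided for each laboratory parameter by randomized treatment group". SAP 8.1 lets unscheduled values into these shift tables. Section 8.5.3 also plans trellis plots of maximum and minimum post-baseline values against baseline, by arm. Neither document restricts these displays to visits common to all arms, allows for the number of draws, or carries a caveat on the unequal schedule.

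**The concern.** A worst value depends on how often one looks. If Arms 1 and 2 are examined three times as often as Arm 3 in the first six weeks, part of any difference in worst grade may reflect the schedule and not the drugs.

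This matters for two reasons. First, SAP 3.2 says "The contributions of BNT111 and cemiplimab will be delineated in single agent calibrator arms (Arms 2 and 3"), and laboratory abnormality within a patient is a secondary safety endpoint in all three arms. The contrast of Arm 1 with Arm 3 shows what BNT111 adds to cemiplimab, and it is the one that crosses the two schedules. Second, protocol 9.4.5 planned a summary of clinically significant abnormal results for each laboratory parameter, but SAP 8.5.3 now produces the abnormality tables for urinalysis only. For hematology and chemistry, the shift table is thus the main per-patient tabulation of abnormality left. The maximum and minimum plots depend on the number of draws in the same way.

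**Working it through.** The documents give no laboratory abnormality rate, so there is no planned figure to reproduce. The draw counts come from the documents. Every rate, correlation and episode length below is an assumption.

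**1. Count of scheduled post-baseline draws through C3D1**
- Arms 1 and 2: days 8, 15, 22, 29, 36, 43, so 6.
- Arm 3: days 22, 43, so 2.
- Each later CnD1 adds one draw in every arm: 11 vs 7 by C8D1, 19 vs 15 by C16D1, 37 vs 33 by C34D1. (The SAP version history gives 34 as the maximum number of cycles.)

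**2. Direction.** Arm 3's draw days are a subset of the other arms' days. For one and the same laboratory course, the scheduled draws of Arm 3 can record an equal or a milder worst grade, never a worse one.

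**3. Which abnormalities are affected.** Take one episode at constant grade lasting D days, with onset uniform over days 1 to 43. The share caught is min(1, D/7) on the weekly schedule and min(1, D/21) on the Arm 3 schedule.
- D = 3: 43% vs 14%
- D = 7: 100% vs 33%
- D = 14: 100% vs 67%
- D = 21 or more: 100% vs 100%

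The bias vanishes for a grade held for about 21 days or longer.

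**4. Independent draws, equal per-draw probability p.** P(grade seen at least once in k draws) = 1 − (1 − p)^k.
- p = 5%: 1 − 0.95^6 = 26.5% vs 1 − 0.95^2 = 9.8%, a gap of 16.7 points. Expected patients flagged by C3D1, with 90/45/45 randomized: 90 × 0.2649 = 23.8, 45 × 0.2649 = 11.9, 45 × 0.0975 = 4.4.
- p = 1%: 5.9% vs 2.0%
- p = 2%: 11.4% vs 4.0%
- p = 10%: 46.9% vs 19.0%

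**5. Correlated draws.** Serial values in one patient are not independent. With a normal random intercept, latent correlation ρ and threshold t = Φ⁻¹(1 − p), the probability is 1 − ∫ φ(z) [Φ((t − √ρ z)/√(1 − ρ))]^k dz. At p = 5% and k = 6 vs 2 this gives 18.6% vs 8.8% at ρ = 0.5, and 11.4% vs 7.2% at ρ = 0.85.

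Gap in percentage points at p = 5%, for patients still on treatment at each visit:

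| Through | Draws | Independent | ρ = 0.5 | ρ = 0.85 |
|---|---|---|---|---|
| C3D1 | 6 vs 2 | 16.7 | 9.8 | 4.2 |
| C8D1 | 11 vs 7 | 13.0 | 5.6 | 1.9 |
| C16D1 | 19 vs 15 | 8.6 | 3.2 | 1.0 |
| C34D1 | 37 vs 33 | 3.4 | 1.6 | 0.5 |

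**6. After restriction to common visits.** The count by C3D1 is 2 vs 2. Equal per-draw rates then give equal expected rates, for example 9.75% vs 9.75% at p = 5% with independent draws.

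**The case against.** The other side has several good points.

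- **No test depends on this table.** SAP 8.1 rules out formal comparisons between groups, and safety is descriptive. This stands and limits the severity. It does not remove the problem, because readers of a side-by-side table have only the raw percentages.
- **The calibrator arms are mainly about response.** Protocol 4.2 ties the contribution of components to ORR. That is fair, but laboratory safety is still a stated secondary objective for all three arms.
- **The table covers all treatment, not six weeks.** This stands: the gap narrows as common visits accumulate. The documents give no treatment durations, and patients who stop or move to add-on early keep the wider gap.
- **Scheduled draws are not the only ones.** Unscheduled values count in this table, and protocol 8.2.5 has clinically significant abnormal values repeated. Extra draws could narrow the gap (if they catch events between Arm 3 visits) or widen it (if more visits prompt more repeats). The net effect is unknown.
- **Equal counts are not equal conditions.** At C2D1 and C3D1, Arms 1 and 2 are drawn about 7 days after a weekly BNT111 dose and Arm 3 about 21 days after cemiplimab. Common visits also drop the weekly values, where a real transient effect may show; protocol 2.1.2 lists transient lymphopenia as an identified BNT111 risk. This stands, so the restricted table cannot replace the full one.

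A reader might infer that cemiplimab alone must look safer by construction. The documents do not support that. The maximum over more draws is at least as large, not necessarily larger, and persistent abnormalities are caught on both schedules.

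**Conclusion.** The concern holds within limits. For hematology and chemistry, the planned worst-grade table is biased toward a milder worst grade in Arm 3 when that arm is compared with Arm 1 or Arm 2 and the grade peak lasts less than about 21 days. The direction for scheduled draws follows from the visit schedule alone. The size cannot be known from the documents: the gaps computed above rest on an assumed equal 5% per-draw rate, and the independent-draws figure is the extreme of the cases shown.

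The contrast of Arm 1 with Arm 2 is untouched because they share a schedule. TSH/T4, coagulation and urinalysis do not follow the weekly visits. By-visit summaries at common visits are also unaffected, although they do not give worst grade per patient.

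It would be going too far to say that the plan attributes the sampling difference to BNT111, since the SAP draws no such inference. It would equally be wrong to read arm differences from a common-visit table alone. This is a cheap improvement to a descriptive safety display.

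**What to change.** In SAP 8.5.3:

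1. Keep the planned shift table unchanged, so that no early signal is hidden.
2. Add a supplementary worst-grade shift table for hematology and chemistry, restricted to scheduled visits common to all three arms: C2D1, C3D1, later CnD1, and EoT where it falls within the on-treatment window. State that window, since 8.5.3 does not spell it out. Do not add SFU1 to an on-treatment table unless the window covers it. State that unscheduled values are excluded from the supplementary table.
3. Footnote both tables and the maximum/minimum trellis plots with the unequal schedule, and say that the two tables are to be read together.

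The cost is a few SAP sentences, a footnote and one more run of an existing table. No visit or blood draw changes. The downside is that the restricted table omits values from the weekly BNT111 phase and can understate transient BNT111 effects, and time since last dose still differs between arms at the common visits. The footnote should say so.

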1.3.2 Schedule of activities for patients receiving add-on therapy (SOA2)

Patients with centrally verified PD on monotherapy in Arm 2 or 3 may enter add-on therapy where eligible patients will receive the other compound in addition to the continued initial trial therapy after re-consent.

SOA2										Po	st-treatment	t follow-up p	period
Cycle=21 d	Baseline add- on therapy	P	Add-on Cycl	e 1		Add-on Cycl	e 2	Add-on Cycle 3 onward	End of treatment ^a	Safet	y FU ^b	Efficacy FU ^c	Survival FU ^d
Visit		AOC1D1	AOC1D8	AOC1D15	AOC2D 1	AOC2D8	AOC2D15	AOCnD1 ^f	EoT	SFU1	SFU2	EFU	LTFU
Day	≤ 10 d prior to AOC1D1	1	8	15	22	29	36	Хâ	0 to 21 d after last dose	30 d after last dose	90 d after last dose	6/9/12 wks	Every 3 mon after last trial assessment
Visit window			±1 d	±1 d	±1 d	±1 d	±1 d	±3 d		+5 d	±7 d	±7/14 d	±14 d
					Asse	ssments an	d procedures	1					
Concomitant medication and therapy ^h	x	X ⁱ	x	х	х	х	x	x	x	х	х		
Informed consent	X												
Vital signs ^j	х	X i	Х	Х	Х	Х	Х	Х	X	Х			
Weight	Х	Х	Х	Х	Х	Х	Х	Х	Х	Х			
Physical examination ^k	х	X ⁱ	х	х	х	х	х	х	х	х			
ECOG PS	Х	χi	Х	Х	Х	Х	Х	Х	Х	Х			
12-lead ECG I	Х	Perform, if clinically indicated							Х				
CT and/or MRI ^{m, n}	x ^m	x ⁿ										x ⁿ	
Brain imaging	Χ°		Χ°									Χ°	

Page 22 of 133 Version: 7.0 Date: 09 FEB 2023

SOA2				Tr	eatment pe	eriod				Po	st-treatmen	t follow-up p	follow-up period	
Cycle=21 d	Baseline add- on therapy	Δ	Add-on Cycl	e 1		Add-on Cyc	le 2	Add-on Cycle 3 onward	End of treatment ^a	Safet	y FU ^b	Efficacy FU ^C	Survival FU ^d	
Visit		AOC1D1	AOC1D8	AOC1D15	AOC2D	AOC2D8	AOC2D15	AOCnD1 f	EoT	SFU1	SFU2	EFU	LTFU	
Day	≤ 10 d prior to AOC1D1	1	8	15	22	29	36	Хâ	0 to 21 d after last dose	30 d after last dose	90 d after last dose	6/9/12 wks	Every 3 mon after last trial assessment	
Visit window			±1 d	±1 d	±1 d	±1 d	±1 d	±3 d		+5 d	±7 d	±7/14 d	±14 d	
Adverse events ^p	x	Χİ	Х	Х	X	Х	Х	X	X	х	X			
PRO/QoL assessments ^q		х			х			Х	х	х				
PGIS		х						AOC4D1, AOC8D1	х					
PGIC								AOC4D1, AOC8D1	х					
Survival status													Х	
Subsequent anti- cancer therapy									X	X	X	X	x	
BNT111 ^r		Х	Χ ^s	Χ ^s	X	Χ ^s	Χ ^s	Х						
Cemiplimab (Q3W) ^t		х			х			Х						
Hematology ^u	Х	Х	Х	Х	Х	Х	Х	Х	Х	Х				
Blood chemistry V	Х	χ ⁱ	Х	Х	Х	Х	Х	Х	Х	х				
Coagulation W	х			Perform	n, if clinically	y indicated			х		if clinically cated			
TSH and free T4 ^X	Х		X							Х				

Page 23 of 133 Version: 7.0 Date: 09 FEB 2023

SOA2				Tr	eatment pe	eriod				Post-treatment follow-up period			
Cycle=21 d	Baseline add- on therapy	Д	Add-on Cycle	e 1		Add-on Cycl	e 2	Add-on Cycle 3 onward	End of treatment ^a	Safet	y FU ^b	Efficacy FU ^C	Survival FU ^d
Visit		AOC1D1	AOC1D8	AOC1D15	AOC2D	AOC2D8	AOC2D15	AOCnD1 f	EoT	SFU1	SFU2	EFU	LTFU
Day	≤ 10 d prior to AOC1D1	1	8	15	22	29	36	Χg	0 to 21 d after last dose	30 d after last dose	90 d after last dose	6/9/12 wks	Every 3 mon after last trial assessment
Visit window			±1 d	±1 d	±1 d	±1 d	±1 d	±3 d		+5 d	±7 d	±7/14 d	±14 d
Pregnancy test ^y	X	X			X			X	X	X			
Urinalysis ^Z	X			Perform	n, if clinically	/ indicated			Х	Х			
Cytokines ^{aa}		Х			Х			X pp					
Cellular immune responses cc	X cc							X cc	X ^{dd}				
HLA haplotyping ^{ee}	x ^{ee}												
Tumor biopsy ff	Χ ^{ff}							X ff					

Note: On treatment days, all assessments should be performed prior to dosing unless otherwise specified.

- a Patients who discontinue trial treatment for whatever reason will return to the clinic for EoT visit within 21 d after last dose. The visit at which response assessment shows (confirmed) progressive disease may be used as the EoT visit. The EoT visit and post-treatment follow-up period will only be performed after discontinuation of both trial drugs.
- b All AEs will be reported until 90 d after the last dose of trial treatment or until a new anti-cancer therapy is started. Additionally, in case a new anti-cancer therapy is started within 90 d after last treatment, the safety follow-up visit should be performed just prior to starting the new anti-cancer therapy. Adverse events after start of new anti-cancer therapy do not need to be reported unless a causal relationship to BNT111-01 or cemiplimab is suspected.
- Patients who discontinue trial therapy prior to disease progression should continue to have regular efficacy assessments as scheduled per protocol, until disease progression, the start of next-line anti-cancer therapy, withdrawal of consent, or death, whichever occur first.
- d After the last trial visit, information on survival status and new anti-cancer therapy will be collected via phone calls, patient medical records, and/or clinic visits approximately every 3 mon until death (unless the patient withdraws consent for survival follow-up or the sponsor terminates the trial). If a patient asks to be withdrawn from survival follow-up, this request must be documented in the source documents and signed by the investigator.
- e Visit AOC1D1 shall occur no longer than 6 wks after confirmed disease progression on monotherapy in Arm 2 or 3.

Clinical Trial Protocol BNT111-01

Page 24 of 133 Version: 7.0 Date: 09 FEB 2023

- f "n" represents the number of the respective cycle (e.g., AOC3 means the third cycle of add-on therapy).
- g Visit X should occur 21 (± 3) d after the first day (i.e., treatment visit) of the previous cycle.
- h Continued record of concomitant medication and therapy after add-on, includes any therapies (e.g., prescription drugs, over-the-counter drugs, vaccines, herbal or homeopathic remedies, nutritional supplements) used by a patient in addition to protocol-mandated trial treatment until the SFU2 visit.
- i If baseline and AOC1D1 are on the same day, assessment only needs to be taken once.
- Vital signs (body temperature, pulse rate, respiratory rate, and blood pressure) should be measured prior to the administration of the trial treatments, and at 30 (±10) min, 60 (±10) min, 4 h (±10 min), and 6 h (±10 min) after administration, or if clinically indicated (see Section 8.2.3 for guidelines on reduction or expansion of these time points).
- k At baseline and at EoT assessments must include a full physical examination. Record abnormalities observed on the respective eCRF pages as appropriate. For all subsequent physical examinations perform a limited, symptom-directed examination at specified time points and as clinically indicated at other time points. Record new or worsened clinically significant abnormalities on the AE eCRF.
- I Single 12-lead ECG recordings will be obtained during baseline, at EoT, and as clinically indicated at other time points. Patients should be resting in a supine position for at least 10 min prior to ECG recording. The interpretation of the ECG recording will be done locally by the investigator.
- m Baseline image may not be older than 21 d prior to AOC1D1. Target lesions and non-target lesions can be redefined at baseline assessment for add-on therapy.
- n Tumor response will be measured by RECIST 1.1 / iRECIST. Patients will undergo tumor assessments every 6±1 wks for the 3 mon after start of add-on treatment, every 9±1 wks for the next 9 mon, and every 12 ± 2 wks thereafter, regardless of dose delays, until (confirmed) disease progression (even if the patients discontinue trial treatment for other reasons) or until the start of next-line anti-cancer therapy (whichever occurs first). An extra scan should be scheduled if clinically indicated.
- o Patients with new brain lesions identified at baseline for add-on therapy cannot continue with add-on therapy, patients with known brain lesions during monotherapy (Arm 2 or 3) should have stable brain lesions at baseline for add-on therapy, the lesions should be followed and assessed at all subsequent tumor assessments. If no brain lesions are present at baseline assessment for add-on therapy, brain imaging does not need to be repeated, only if clinically indicated as per investigator judgment.
- All AEs will be documented in the eCRF, and all SAEs should be reported to the sponsor within the appropriate time frame. All AEs will be reported until 90 d after the last dose of trial treatment (i.e., SFU2 visit). In addition, the sponsor should be notified (even after SFU2 visit), if the investigator becomes aware of any serious AE that is believed to be related to prior exposure to trial treatment or a trial procedure.
- q Patient-reported outcomes/quality of life assessment questionnaire must be completed before any assessments are done or any treatment is given on the dosing day. Patients will provide PRO/QoL assessments during trial visits at baseline for add-on therapy, AOC3D1, AOC3D1, AOC4D1, every 9±1 wks for the next 9 mon, and every 12±2 wks thereafter until SFU1.
- r After administration of BNT111, initially an observation time of at least 6 h is required (see Section 6.8.4.1). Treatment to be continued up to 24 mon or until confirmed disease progression, unacceptable toxicity or patient withdrawal of consent.
- s Weekly dosing applicable to patients who have received cemiplimab monotherapy (Arm 3). Also applicable to patients who have received BNT111 monotherapy (Arm 2) if the patient has previously received ≤ 4 doses of BNT111.
- t Cemiplimab will be given according to valid Prescribing Information in the country every 3 wks (±3 d). The first administration of cemiplimab will be on Cycle 1 Day 1, followed by every 3 wks (±3 d) thereafter. Cemiplimab will be administered subsequently after administration of BNT111 with at least 30 min interval. There should be an initial observation time of 6 h after administration of cemiplimab. From the second administration of cemiplimab, no observation time is stipulated with reference to cemiplimab (local protocol should be followed). Treatment to be continued up to 24 mon or until confirmed disease progression, unacceptable toxicity or patient withdrawal of consent.
- u Hematology assessment should be performed at baseline for add-on therapy, ≤ 24 h prior to each drug administration, on treatment discontinuation, and at 30 d SFU1 or if clinically indicated (see Section 10.2 for assessments to be done). Samples should be assessed by both the central and local laboratory. Results of local laboratory assessments need to be reviewed prior to drug administration. Unscheduled assessments can be performed locally or sent to the central laboratory.

Clinical Trial Protocol BNT111-01

Page 25 of 133 Version: 7.0 Date: 09 FEB 2023

- Chemistry panel should be performed at baseline for add-on therapy, ≤ 24 h prior to each drug administration, on treatment discontinuation, and at 30 d SFU1 or if clinically indicated (see Section 10.2 for assessments to be done). Samples should be assessed by both the central and local laboratory. Results of local laboratory assessments need to be reviewed prior to drug administration. Unscheduled assessments can be performed locally or sent to the central laboratory.
- w Coagulation assessments are to be performed at baseline for add-on therapy, at EoT, and if clinically indicated (see Section 10.2 for assessments to be done). Samples should be shipped to a central lab; unscheduled assessments can be performed locally.
- x TSH and free T4 will be assessed at baseline for add-on therapy, once every two cycles, on treatment discontinuation, and at SFU1. Samples should be shipped to a central laboratory and, if required, to the local laboratory. Unscheduled assessments can be performed locally or sent to the central laboratory.
- y All WOCBP will have a serum pregnancy test at baseline, within 10 d prior to initiation of trial treatment. Urine or serum pregnancy test will be performed at the start of every cycle (starting from Cycle 2) or according to local requirements (in cases where more frequent testing is required) and at EoT and SFU1. If a urine pregnancy test is positive, hold dosing and confirm the result with a serum pregnancy test.
- z For urinalysis assessments dipsticks are to be used, microscopic evaluation should be performed per investigator's discretion.
- aa Peripheral blood for assessment of cytokines will be drawn from all patients prior to administration of BNT111 and 4 to 6 h post application. The tests will be performed centrally. This is only applicable for the first three cycles with BNT111, if cytokines were collected in Arm 2 for three cycles, no further cytokines need to be collected.
- bb Only applicable for Cycle 3.
- cc At selected trial sites, as part of the biomarker sub-study, blood for isolation of PBMCs for analysis of cellular immune responses should be taken during baseline (unless previous blood draw was < 7 wks, then the baseline sample can be omitted) and on AOC3D1, AOC5D1, AOC8D1, every six cycles afterwards, and at EoT. This applies only to patients in Arm 2 and Arm 3 add-on therapy who have consented to the biomarker sub-study.
- dd Should be done within 3 wks after BNT111 administration.
- ee Only for patients entering Arm 3 add-on therapy who have not yet provided a sample for HLA typing: a blood sample for HLA typing should be taken which should be stored at -80°C.
- At selected trial sites, as part of the biomarker sub-study, optional biopsies at baseline, under treatment and at progression will be performed. The tumor biopsy will be performed, if considered clinically feasible by the investigator. This applies only to patients in Arm 2 and Arm 3 add-on therapy who have consented to the biomarker sub-study. The tumor sample can be from a core biopsy or from resected tumor tissue. Fine needle aspirates and cytological specimens are not acceptable. In patients who have had biopsies taken during BNT111 monotherapy, the number of biopsies during add-on is to be adjusted as appropriate (up to three in total during the duration of the trial). It is recommended to perform the biopsy on progression only if 4 wks or more have elapsed since the last biopsy (on-treatment biopsy). If the time is shorter, no biopsy on progression should be taken.

For other trial sites, if any biopsies or resections are to be performed as part of standard clinical care, tissue samples from such procedures should be provided (if feasible) for the sponsor for biomarker testing.

Abbreviations: AOCnDn = add-on, cycle "n", day "n"; d = day; CT = computer tomography; ECG = electrocardiogram; ECOG PS = Eastern Cooperative Oncology Group Performance Status; d = day(s); eCRF = electronic case report form; EoT = end of treatment; FU = follow-up; h = hour(s); LTFU = Lost to follow-up; mon = month; MRI = magnetic resonance imaging; PGIC= Patient Global Impression of Change; PGIS= Patient Global Impression of Severity; PRO/QoL = patient-reported outcomes/quality of life; SOA = schedule of activity; T4 = Thyroxine; TSH = thyroid-stimulating hormone; wks = week(s); WOCBP = women of childbearing potential.

Clinical Trial Protocol BNT111-01

Page 26 of 133 Version: 7.0 Date: 09 FEB 2023

TABLE OF CONTENTS

1	PROTOCOL SUMMARY	3
1.1	Trial synopsis	3
1.2	Schema (graphical representation of the trial)	10
1.3	Schedules of activities	11
1.3.1	Schedule of activities for Arm 1, Arm 2, and Arm 3 patients (SOA1)	11
1.3.2	Schedule of activities for patients receiving add-on therapy (SOA2)	21
TABLE (OF CONTENTS	26
LIST OF	TABLES	30
LIST OF	FIGURES	31
TRIAL-S	PECIFIC ABBREVIATIONS	31
2	INTRODUCTION	33
2.1	Background	33
2.1.1	Treatment option overview for unresectable Stage III and Stage IV and recurrent melanoma	33
2.1.2	Introduction to the investigational treatments	35
2.2	Trial rationale	37
2.3	Benefit/risk assessment	38
2.3.1	Risk assessment	38
